During hospitalization, data will be recorded from ED pulse check, and EPIC regarding fluid administration, transfusion of pRBC, initial hematocrit, times and types of procedures (e.g. upper endoscopy, enteroscopy, colonoscopy etc), time from entry to ED and CDU, to time to localization of source of bleeding, admission disposition discharge from CDU, regular floor, ICU), time of discharge. The procedures involved in the hospitalization (i.e. upper endoscopy, enteroscopy, and colonoscopy) will be done as part of standard of care. All of this information will be linked to the subject's study ID number as described above. This data collection is for research purposes only.

In addition, the costs of the procedures will be collected through financial services. The costs that will be collected are both the fixed and variable costs associated with each patient in the study. We will also collect the direct and indirect costs allocated to each patient. All charges associated with the admission for each patient in the study will have costs allocated. This will be evaluated as an additional data point to compare the two arms of the study. No additional PHI will be collected.

Telephone Follow-Up

Those subjects discharged from the CDU will be contacted the following day by phone by a research staff member to make sure that they are doing well and that the appropriate follow up procedure has been arranged. Each patient will be called 30 days after discharge to check to see if bleeding has recurred. Please see attached form for telephone script that staff member will read along with particular questions that will be asked.

No more than three attempts will be made at each time point to reach the subject. If a message is left, it will be "Hello, this is [name] calling from UMass looking to speak with [subject]. Please call back at [number] at your earliest convenience. Thank you."

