12. DATA AND SPECIMEN BANKING*

Not applicable.

13. Data Analysis and Management*

- Data analysis plan: As discussed above, data will be obtained through review of medical records. Specifically, we will be looking at time to detection of active bleeding or visualization of stigmata of recent bleeding such as adherent blood clot or a visible vessel, laboratory values, number of blood products transfused procedures performed, along with additional measures as described above. Once we have separated our two cohorts we will perform chi-square and standard t-tests to compare the different dependent variables in the two cohorts. We will also perform a Kaplan-Meier curve analyses to compare length of stay and time to diagnosis which is the primary metric of this study.

INVESTIGATOR STUDY PLAN - H00015196

- Steps that will be taken to secure data: All clinical data from individual subjects will be de-identified and given a study number. The study number will serve as a link between the data and the subject's identifiable information. RedCAP online encrypted database will be used to store the dataset. The database will only be accessed by the primary investigator and research assistants.
- Data will be exported for analysis as a de-identified data set. The de-identified dataset (which would be absent of any PHI) will remain at UMass under password access by the PI and sub-investigators.
- Identifier keys will be destroyed once primary data analysis is complete.
- No identifying information will be used in any report or publication generated from this study.
- Power analysis: Based on our recent randomized trial of NHGIB of VCE v SOC, we were able to detect a very significant difference in the rate of active bleeding with 36 patients in each arm, Hazard ratio 2.7. J Sung et al. used the same sample size in their randomized trial for H bleeding to similar effect. We thus plan on using 40 patients in each arm for each group. The increase to 40 from 36 is used to cover any technical failures or incompletely studied patients.

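### Cost, and possibly procedure counts, are framed around the index admission, so deferred outpatient endoscopy and the study-paid capsule may go uncounted

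*Protocol*

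**What the plan says.** **Endpoints.** Protocol section 10 lists cost as a secondary endpoint and names it by the admission. It also lists the numbers of invasive and of therapeutic procedures, with no time window.

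**Cost collection (section 11, Review and Follow-Up).** The wording varies in breadth. The broader statements are that "the costs of the procedures will be collected through financial services" and "The costs that will be collected are both the fixed and variable costs associated with each patient in the study", followed by a line on direct and indirect costs per patient. The allocation rule is narrower: "All charges associated with the admission for each patient in the study will have costs allocated". The paragraph ends "No additional PHI will be collected".

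**Procedure collection.** Section 11 says "During hospitalization, data will be recorded from ED pulse check, and EPIC regarding fluid administration, transfusion of pRBC, initial hematocrit, times and types of procedures". Section 13 lists, from medical-record review, "number of blood products transfused procedures performed, along with additional measures as described above", without an inpatient limit.

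**Follow-up calls (section 11).** Patients discharged from the CDU are called the next day to check, among other things, "that the appropriate follow up procedure has been arranged". Later, "Each patient will be called 30 days after discharge to check to see if bleeding has recurred". The telephone script is an attachment that is not among the documents.

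**Where endoscopy takes place.** In the capsule arm, section 11 allows EGD or colonoscopy as an outpatient within 72 hours after a capsule study that shows no blood. Colonoscopy may also be deferred to outpatient care when blood is seen in the right colon and active bleeding has stopped. Sections 4 and 11 say that SOC patients are admitted.

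**Who pays for the capsule.** Section 29 says that the study pays for the capsule and its reading in either arm and does not bill them.

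**The concern.** A pathway meant to send some patients home and scope them later needs an outcome window that extends past discharge. If procedures and costs are taken from the index admission only, an endoscopy done during an SOC admission is counted, while the same endoscopy done two days after a capsule patient goes home is not. Work that was moved then looks like work that was avoided.

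The capsule raises a parallel problem. A cost built from charges has no charge to pick up for an item that is never billed. Every early-capsule patient receives that item, and section 11 expects only a few SOC patients to do so. The cost comparison could therefore leave out the intervention being tested.

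These results matter to the sponsor. Section 4 sets out to examine reductions in procedures and hospital costs, and section 16 states fewer procedures as a hypothesis.

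**Working it through.** The documents give no expected value for either endpoint, so there is no figure to reproduce. The check compares the passages and then gives a scale.

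**1. Passages side by side**

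| Item | Points to admission only | Points wider | States a window? |
|---|---|---|---|
| Cost | Endpoint name (section 10); allocation rule (section 11) | Procedure costs and per-patient costs (section 11) | No |
| Procedure count | Collection sentence tied to the hospital stay (section 11) | Endpoint (section 10) and record review (section 13), both unlimited | No |
| Capsule and reading | Not billed (section 29) | Earlier trial's cost result reported as holding even with the capsule added (section 5) | Not named as a cost item |

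**2. Capsules, if left uncosted**

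Inputs: 40 patients per arm per group (section 13). SOC capsule use, p, is not given, so two proxies are used for NHGIB: the 4–10% expected to have small-intestinal bleeding (section 11), and 36/336 = 10.7% observed capsule use across all GI bleeding (section 5). For hematemesis, p = 0 is assumed, because section 11 describes SOC capsules under NHGIB.

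Excess of early-capsule over SOC capsules per group = 40(1 − p):

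- NHGIB, p = 0.04: 38.4
- NHGIB, p = 0.10: 36.0
- NHGIB, p = 0.107: 35.7
- Hematemesis, p = 0: 40

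Both groups together: 40 + 35.7 = 75.7 to 40 + 38.4 = 78.4. All 80 early capsules would be uncosted. The 76 to 78 is the excess over SOC. No unit cost is given, so this cannot be turned into money.

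**3. Deferred endoscopies, if left uncounted**

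Inputs: 30% of the hematemesis cohort cited in section 5 could be discharged after the capsule. Let q be the share of discharged patients who have one outpatient endoscopy, taken as equal in both arms, and s the share of SOC patients discharged before endoscopy. Neither is given.

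Net undercount per patient = q(0.30 − s); multiply by 40 for an arm:

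| q | s | Per patient | Per 40 |
|---|---|---|---|
| 1 | 0 | 0.30 | 12 |
| 0.5 | 0 | 0.15 | 6 |
| 1 | 0.15 | 0.15 | 6 |
| 1 | 0.30 | 0 | 0 |
| 0 | any | 0 | 0 |

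For NHGIB the documents give no discharge share, so using the same range there is an assumption. The right-colon route applies to NHGIB only, since the hematemesis recording stops once the capsule enters the small bowel (section 11).

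**4. What is known about s**

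Section 5 reports that nearly 30% of patients admitted at this hospital had no inpatient endoscopy. It does not say how many had one later as outpatients. Sections 5 and 29 allow discharge without admission in either group, against sections 4 and 11. A value of s near 0.30 is therefore plausible, and it brings the net figure close to 0.

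**5. Can existing contacts cover a 30-day window?**

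Section 9 gives participation as hospital stay plus 30 days, about 31–40 days. A call 30 days after discharge therefore falls on or after day 30 from randomisation.

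**The case against.** The strongest reply is that the documents show an unstated window, not an exclusion. Section 10 puts no admission limit on the procedure count and neither does section 13. The hospital-stay sentence in section 11 lists what is recorded in hospital without saying that later procedures are ignored. This stands: only cost is named by the admission.

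On the capsule, who is billed is not the same as what is costed. Section 11 collects fixed, variable, direct and indirect costs per patient, and section 5 suggests that the earlier trial counted the capsule. This also stands as evidence of intent, but no available passage says that the capsule, or outpatient endoscopy, enters the cost.

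A reader might infer that the procedure comparison is biased toward the capsule arm by about 12 per 40. The documents do not support that. Twelve requires every discharged patient to be scoped, although sections 5 and 11 make outpatient endoscopy conditional on need, and it requires no deferral under SOC. The hospital's own figure of nearly 30% without inpatient endoscopy points to possible similar deferral.

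Two further points are fair. Index-admission cost is a legitimate hospital-perspective measure and matches the aim in section 4. And the DSMB charter (the document supplied as the SAP), section 9, says that a SAP will define all calculated variables. A window may appear there or in the unseen telephone script, but neither supplies one in the available text.

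**Conclusion.** The point holds in limited form. The cost endpoint is framed around the admission. The procedure count has no window, and its only timed collection sentence refers to the hospital stay. Followed as written, this can count deferred endoscopy as avoided and leave out the study-paid capsule and reading.

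For the capsule, any omission would be almost wholly one-sided: all 80 early capsules, an excess of about 76 to 78 over SOC, assuming 4–10.7% SOC use in NHGIB and none in hematemesis. For procedures, neither direction nor size is established. The illustrative range is 0 to 12 per 40, near 0 if SOC defers similarly. Both figures apply only if the items are in fact not captured.

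It would go too far to say that the plan excludes these items, or that the trial's main result is at risk. Time to detection and the sample size are unaffected; only secondary endpoints are involved. It should be fixed, because the remedy is cheap and section 13 has identifier keys destroyed after the primary analysis, which may make later retrieval impossible.

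**What to change.** - In both arms, count invasive and therapeutic procedures, inpatient or outpatient, from randomisation to day 30, using EPIC, financial services and the existing 30-day call.
- Add one standard unit cost for capsule plus reading to every patient in either arm who received a capsule.
- Report 30-day cost alongside index-admission cost.
- Write these definitions into the SAP that the DSMB charter, section 9, says will define calculated variables.
- Reconcile Protocol sections 4 and 11 with sections 5 and 29 on whether SOC patients can be discharged without admission, since this decides whether SOC procedures can also be deferred.
- Leave the follow-up for rebleeding at 30 days after discharge.

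**Cost.** Endpoint wording, a few extra data fields, retrieval of outpatient costs, and a check that this fits the statement "No additional PHI will be collected". No new patient contact is needed. Data on care outside the hospital system will be incomplete, and self-report is limited by the cap of three call attempts. The capsule result may look less favourable.

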12. DATA AND SPECIMEN BANKING*

Not applicable.

13. Data Analysis and Management*

- Data analysis plan: As discussed above, data will be obtained through review of medical records. Specifically, we will be looking at time to detection of active bleeding or visualization of stigmata of recent bleeding such as adherent blood clot or a visible vessel, laboratory values, number of blood products transfused procedures performed, along with additional measures as described above. Once we have separated our two cohorts we will perform chi-square and standard t-tests to compare the different dependent variables in the two cohorts. We will also perform a Kaplan-Meier curve analyses to compare length of stay and time to diagnosis which is the primary metric of this study.

INVESTIGATOR STUDY PLAN - H00015196

- Steps that will be taken to secure data: All clinical data from individual subjects will be de-identified and given a study number. The study number will serve as a link between the data and the subject's identifiable information. RedCAP online encrypted database will be used to store the dataset. The database will only be accessed by the primary investigator and research assistants.
- Data will be exported for analysis as a de-identified data set. The de-identified dataset (which would be absent of any PHI) will remain at UMass under password access by the PI and sub-investigators.
- Identifier keys will be destroyed once primary data analysis is complete.
- No identifying information will be used in any report or publication generated from this study.
- Power analysis: Based on our recent randomized trial of NHGIB of VCE v SOC, we were able to detect a very significant difference in the rate of active bleeding with 36 patients in each arm, Hazard ratio 2.7. J Sung et al. used the same sample size in their randomized trial for H bleeding to similar effect. We thus plan on using 40 patients in each arm for each group. The increase to 40 from 36 is used to cover any technical failures or incompletely studied patients.

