5. BACKGROUND*

After 40 years of considering gastrointestinal bleeding as upper or lower and largely ignoring the small intestine, there is accumulating evidence that the conventional approach to the assessment of NHGIB could be improved by early deployment of a video capsule as the first diagnostic test. Currently, video capsule endoscopy is considered the gold standard diagnostic test for small intestinal bleeding after upper and lower endoscopy. However, we feel that video capsule endoscopy is an underutilized, minimally invasive tool that can improve rates of detection, minimize patient discomfort, and shorten the length of hospital stay for many patients. In a recent study at UMass of 336 patients who presented to the ED with complaints of gastrointestinal bleeding only 36 patients (10.7%) were given a video capsule during their stay.¹

Traditionally, in patients with hematemesis, upper endoscopy has been the diagnostic and therapeutic modality of choice. However, recent data from a randomized clinical trial by Sung et al suggests that when video capsule endoscopy is used as the primary diagnostic tool, the investigators were able to safely define those patients that require admission from those that can be discharged for later follow-up². In this cohort, 30% of patients could be safely discharged and undergo endoscopy, if necessary within 48 hours, as an outpatient. This data is consistent with our internal epidemiological data from UMass where nearly 30% of patients who were admitted did not receive any endoscopic evaluation as in-patients.

Similarly, in a randomized controlled trial, we have recently shown that patients with NHGIB may benefit from early VCE. In this population, the detection of active bleeding with video capsule as the first procedure was 63% compared with 27% for the standard of care approach. We did not demonstrate a significant reduction in length stay since this was not part of the trial design. No attempt was made to change physician behavior. The study was too small to demonstrate a reduction in procedures, but there was a modest reduction in healthcare costs despite the addition of the video capsule. We encountered no adverse events in the study. Readmission rates were not significantly reduced but there were no readmissions in the capsule group for G.I. bleeding where there were four in the standard of care group.

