10. STUDY ENDPOINTS*

- The primary endpoint will be time to detection of active bleeding or stigmata of recent bleeding [blood clot or visible vessel].
- Secondary endpoints will include, admission rate, hospital length of stay, number of invasive procedures, blood product transfusions, number of therapeutic procedures, complication rates, costs of admission, and readmission rates

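### The supplied plan names only unadjusted comparisons; prespecified adjustment of the continuous and count secondary outcomes for pre-randomization hematocrit is a cheap efficiency gain of unknown size

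*Protocol*

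**What the plan says.** **Endpoints (Protocol, Section 10).** "The primary endpoint will be time to detection of active bleeding or stigmata of recent bleeding". The secondary endpoints are "admission rate, hospital length of stay, number of invasive procedures, blood product transfusions, number of therapeutic procedures, complication rates, costs of admission, and readmission rates".

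**Analysis (Protocol, Section 13).** "we will perform chi-square and standard t-tests to compare the different dependent variables in the two cohorts". For the time variables the plan is "Kaplan-Meier curve analyses to compare length of stay and time to diagnosis which is the primary metric of this study". No regression model, stratified test or covariate is named.

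**Hematocrit (Protocol, Section 11, Review and Follow-Up).** The items recorded during the stay include "transfusion of pRBC, initial hematocrit, times and types of procedures". The text does not say whether the value precedes randomization, or whether every patient has one. Section 13 also lists laboratory values among the data to be examined, without giving them a role.

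**Size.** "We thus plan on using 40 patients in each arm for each group". Section 11 randomizes the hematemesis (H) and non-hematemesis (NHGIB) groups separately. Section 13 does not say whether they are also analysed separately.

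**SAP.** The document filed as the SAP is a DSMB charter. Its Section 9 refers to a SAP that will hold the analysis procedures; that SAP is not among the supplied documents.

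**The concern.** Each bleed group is small, and several secondary outcomes (units transfused, procedures, stay, cost) vary widely between patients for reasons unrelated to arm. A severity measure taken before randomization can remove part of that variation without more patients. Hematocrit is an obvious candidate, above all for transfusion, and the trial already records it. The supplied analysis text leaves it unused.

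At stake is the width of the confidence intervals for the secondary outcomes. Section 5 says the sponsor's previous trial was too small to show fewer procedures. That trial had 36 per arm (Section 13) and this one has 40 per arm in each group, so unused information matters most for these outcomes. Naming the covariate now also rules out choosing one after the results are seen.

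**Working it through.** **Inputs from the documents.** 40 per arm in each bleed group, raised from 36 (Section 13). Prior result: "a very significant difference in the rate of active bleeding with 36 patients in each arm, Hazard ratio 2.7". Prior detection rates: "the detection of active bleeding with video capsule as the first procedure was 63% compared with 27% for the standard of care approach" (Section 5).

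**Assumed, because not given.** Two-sided alpha 0.05; 80% power; r between hematocrit and each continuous outcome from 0.1 to 0.5; for time to detection, a log hazard ratio of 0 to 1.0 per SD of hematocrit.

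**1. The plan's own sample size.** The 36 is a precedent with no alpha or power stated, so it cannot be strictly reproduced. It is compatible with the assumed values:
- Two proportions, 63% v 27%: 29 per arm, or 35 with continuity correction.
- Schoenfeld, HR 2.7: 4 × (1.960 + 0.842)² / (ln 2.7)² = 4 × 7.849 / 0.987 = 31.8, so 32 events. With detection averaging (63% + 27%)/2 = 45%, that is 32 / 0.45 / 2 = 35.6 per arm.
- The increase for losses: 36 / (1 − 0.10) = 40, where the 10% is inferred.

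**2. Continuous outcomes, 40 per arm.** The detectable difference without adjustment is (1.960 + 0.842) × √(2/40) = 0.626 SD. A linear model with one baseline covariate multiplies this by √(1 − r²), and the equivalent sample is 40/(1 − r²).

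| r (assumed) | Variance cut r² | Detectable difference | Equivalent per arm | Power at 0.626 SD |
|---|---|---|---|---|
| 0 | 0% | 0.626 SD | 40.0 | 80.0% |
| 0.1 | 1% | 0.623 SD | 40.4 | 80.4% |
| 0.2 | 4% | 0.614 SD | 41.7 | 81.6% |
| 0.3 | 9% | 0.598 SD | 44.0 | 83.6% |
| 0.5 | 25% | 0.543 SD | 53.3 | 89.9% |

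The table ignores the cost of estimating the covariate. With 2n = 80, that multiplies the standard error by √((2n − 3)/(2n − 4)) = √(77/76) = 1.007. The net standard-error ratios are then 1.007 (r = 0), 1.002 (0.1), 0.986 (0.2), 0.960 (0.3) and 0.872 (0.5). Break-even is at r² = 1/77, or r of about 0.11.

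**3. Time to detection.** Simulated Cox models with 40 per arm, conditional HR 2.7, about 45-47% of patients with an event, and 2,000 runs per row. Estimates and standard errors are medians.

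| Covariate log-HR per SD | Power unadjusted → adjusted | SE of log-HR | Estimated log-HR |
|---|---|---|---|
| 0 | 82% → 81% | 0.361 → 0.364 | 0.991 → 0.999 |
| 0.2 | 82% → 83% | 0.362 → 0.365 | 1.000 → 1.027 |
| 0.4 | 79% → 82% | 0.357 → 0.361 | 0.943 → 1.005 |
| 0.7 | 74% → 83% | 0.348 → 0.356 | 0.891 → 1.009 |
| 1.0 | 66% → 84% | 0.342 → 0.353 | 0.801 → 1.013 |

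The standard error does not fall in any row. Power rises because the adjusted estimate is no longer pulled toward zero: ln 2.7 = 0.993 is the conditional value, and the unadjusted model estimates a smaller marginal one.

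**The case against.** The strongest case on the other side is that nothing here is an error. Randomization makes the unadjusted tests valid, no correlation is documented, and at r near 0.1 adjustment gains nothing. All of that stands, and it limits the point to an efficiency suggestion.

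A reader might infer more than the documents support:
- **That the primary endpoint loses precision.** It does not: the standard error of the log hazard ratio is slightly larger after adjustment. The gain is in power, and the estimand changes to a conditional hazard ratio.
- **That chance imbalance biases the results.** At 40 per arm, a difference above 0.25 SD on a given baseline variable has a probability of about 26% (0.25/√(2/40) = 1.12). The unadjusted standard error already allows for this.
- **That hematocrit is a clean baseline value on everyone.** The word initial suggests an early value, but Section 11 does not place it before randomization, fluids or transfusion.
- **That a large gain can be expected.** A gain like that at r = 0.5 is an assumption for every outcome. The link is most plausible for transfusion; for stay, cost and detection it is conjecture.
- **That every comparison in the trial is unadjusted.** This can be said only of the supplied text, since the charter points to a SAP not seen here. Equally, nothing supplied shows that adjustment is planned there.

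The r² formula also belongs to linear models. It does not carry over directly to count models or to the chi-square endpoints.

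**Conclusion.** The point holds as an efficiency improvement for the continuous and count secondary outcomes. The supplied plan is unadjusted and leaves unused a value it already records.

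Under a linear model with 40 per arm, the variance falls by 1-4% at r of 0.1-0.2, 9% at 0.3 and 25% at 0.5. One degree of freedom, about 0.7% of the standard error, is the price if r is zero. The true r is unknown, so the gain may be negligible or worthwhile; the possible loss is trivial.

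For time to detection, power changes by about 0-4 points for a weak to moderate covariate (from −1 point when it is unrelated), and rises by 9-18 points only if hematocrit is strongly prognostic. These figures assume two-sided 0.05 and, for the Cox rows, HR 2.7. The recommendation rests on using a value that truly precedes randomization.

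**What to change.** In Section 13, and in the SAP to which the charter refers, state before any comparative data are reviewed that:

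1. Within each separately randomized bleed group, units transfused, number of procedures, length of stay and cost are compared by regression on arm and the last hematocrit before randomization, as the only covariate.
2. The model form is fixed now for each outcome, not chosen after looking at skewness. For example, use linear regression with robust standard errors where a mean difference is wanted (stay, cost), or a count model where a rate ratio is wanted (units, procedures). Report the adjusted effect with its 95% CI.
3. The unadjusted tests are kept as sensitivity analyses. The chi-square comparisons and Kaplan-Meier curves can stay as they are.
4. A rule covers any patient without a pre-randomization value, for example the bleed-group mean calculated without regard to arm.
5. Optionally, a Cox model with arm and the same covariate supports the time-to-detection analysis, labelled as estimating a conditional hazard ratio. The plan has no regression model for this endpoint, so it would be a new model.

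The cost is a short addition to the analysis text and a check that the hematocrit recorded is the pre-randomization one. If it is not, one item has to be taken from the medical record. No extra patients are needed.
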